## 7.3 Study procedures

## 7.3.1 Selection procedure

## 1. Patient screening

Patient screening will primarily rely on screening by the principal investigator or from other neurologists in the Reinier de Graaf hospital. The treating physician can select his/her patients which are deemed suitable, to inform about them about the study. To avoid overlooking suitable candidates and in case the number of manual screened patients are not sufficient, CTcue – a software extension within the hospital's EPD used for searching patients – is used to perform an additional screening of the patients in the database, based on several criteria from the inclusion and exclusion protocol. Here, for instance, patients can be excluded who have the wrong tremor diagnoses.

Patients in CTcue will be pseudonymized, and will receive a unique identifier number. Only the attending neurologist will have access to the translation key. It is assumed that most of the patients fall within the scope of the principal investigator, because of his specialism on movement disorders within the Reinier de Graaf hospital.

In case the screened patients are attended by a different neurologist, permission will be obtained to get access to the file.

Besides screening via the Reinier de Graaf hospital, a brochure will be used to recruit additional patients suitable for the study. This brochure will be shared via appropriate (social) media channels, or to affiliated neurologists from other Dutch hospitals. In this way, ET patients outside of the Reinier de Graaf hospital can themselves, independent from their physician, contact the investigator(s) directly for more information. To filter out requests, the investigator will ask a few elementary questions from the inclusion criteria (e.g.: "Are you diagnosed with ET") to validate if patients should receive a formal patient information form.

## 2. Pre-selection of patients

Eligible patients will receive patient information and informed consent via mail. Furthermore, Bain and Findley's ADL questionnaire will be added in the application form, together with additional questions to check for the other inclusion and exclusion criteria. Patients will also be provided with a reply envelope in which they can return the questionnaires free of charge, if they want to participate. Additionally, if a patient is willing to participate, he/she fills out the application form and returns it by mail within two weeks. These patients will be checked for eligibility by the investigator. Patients who meet all the preliminary inclusion criteria will be contacted by phone to schedule an appointment for

the next step in the inclusion process. In case the patient has not responded in two weeks, he/she will receive a reminder letter via mail. Patients who returned the application form, but do not meet the inclusion criteria, will be informed via phone that they are not eligible for participation. If patients have additional questions, they can always contact the principal investigator or independent experts.

## 3. Inclusion of patients

The next step requires a visit to the hospital; this appointment will last for a maximum of one hour and takes place at the neurology department of the Reinier de Graaf hospital in Delft. Time will be taken to make the patient feel at ease, to make sure that the patient is not nervous or stressed which may increase tremor severity. The patient is allowed to drink something at this moment (caffeine and alcohol free). This is also when the procedure will be explained and allows a moment for the patient to ask questions. During this appointment, patients will be asked to perform the 7 selected TETRAS tasks (see Section 7.3.4), which will be videorecorded. Two synchronized webcams will record the tasks, which will be done for both the left and the right side. The IMU sensors will be attached on the wrist and hand to record the motion data (see Section 7.3.3). If the patient seems suitable for testing the orthosis, the IMU and video recordings will be used to indicate the tremor severity of the patient without orthosis (baseline).

The hand and upper arm circumference will also be measured by the investigator, these can later be used to select the correct size of the orthosis (S, M, L). If, after this step, the judgement can be drawn that the patient is suitable for the study, meaning that all inclusion- and exclusion criteria (see Section 4.2 and 4.3) are fulfilled, the assessment with the orthoses will directly follow. In preparation for this intervention, it will be determined which arm will be tested, including which size. If only one side turns out to be eligible (left or right), then that side shall be used to test the intervention. If both sides are eligible, the dominant arm as defined by the patient shall be used.

After the TETRAS tasks in baseline condition, the video recordings will be assessed by the principal investigator, where tremor severity and dominant tremor DoF is evaluated.

## 7.3.2 Introduction to the intervention

Figure 4. Global time planning of the testing with the orthosis.

The assessment will last for maximum two hours and takes place at the neurology department of the Reinier de Graaf hospital in Delft. A global time planning can be found in Figure 4. When a patient comes in, the procedure of the study will be explained to prepare the patient for what is coming. Time will be taken to make the patient at ease, to make sure that the patient is not nervous or stressed which may increase tremor severity. The patient is allowed to drink something at this moment (caffeine and alcohol free).

## 7.3.3 Sensor placement and amplitude assessment

The investigator attaches the IMU sensors (Xsens MTw Awinda), which record motion data, to the subjects' wrist and hand. The first sensor is attached to the middle and ring finger with a Velcro strap. The second sensor is attached ventral side of the wrist, also with a Velcro strap. See Figure 5.

*Figure 5:* Placement of Xsens motion sensors on the ventral side of the wrist and the middle and ring finger

Hereafter, the arm motion, and also the tremor amplitude, can be recorded when the investigators enable the sensors in the software package, which includes APIs for connecting with their hardware. This motion data will only be collected while performing different movements and postures as explained below.

## 7.3.4 Tremor severity assessment using TETRAS

The principal investigator will quantify the tremor severity using the TETRAS scale. The principal investigator is adequately trained to carry out this assessment. To minimize investigator bias, a second opinion from an independent neurologist will be consulted. These movements and postures are derived from the TETRAS scale  and patient will be asked to perform them for 30 seconds:

- **Eating with a spoon:** Using a spoon to bring peas from a bowl on the table to the mouth. This is an adaptation from the TETRAS scale, as it usually does not specify which solids or liquids must be used to assess eating with a spoon.
- **Drinking from a cup:** Bringing a cup (8 cm tall, filled with water to 1 cm from top) from the table to the mouth to drink water.
- **Pouring:** Pouring a water filled plastic cup (8 cm tall, filled with water to 1 cm from top) into another cup (8 cm tall) that is unsupported on the table.
- Forward outstretched posture: Subjects will bring their arms forward, slightly lateral to midline and parallel to the ground. The wrists should also be straight and the fingers abducted so that they do not touch each other (Figure 6).
- Lateral "wing beating" posture: Subjects will abduct their arms parallel to the ground and flex the elbows so that the two hands do not quite touch each other and are at the level of the nose. The fingers are abducted so that they do not touch each other (Figure 6).

Figure 6. Forward outstretched posture

Lateral wing beating posture

- **Finger-nose-test:** Subjects extend only their index finger. They then touch the examiners finger located to the full extent of their reach, which is located at the same height (parallel to the ground) and slightly lateral to the midline. Subject then touch their own nose (or chin if the tremor is severe) and repeat this back and forth.
- Archimedes spiral: Subjects are asked to copy an Archimedes spiral using a ballpoint pen that approximately fills an A6 sheet of paper (Figure 7). The lines of the spiral should be approximately 1.3 cm apart. The pen should be held in such way that no part of the limb touches the table.

*Figure 7.* Archimedes spiral. The patient will be asked to draw a spiral between the lines, connecting the two dots.

While performing the tasks for 30 seconds each, motion data is collected simultaneously with the video footage. These are all recorded in the digital CRF and stored on a secure network drive.

## 7.3.5 Cross-over test procedure

The study is designed to be a cross-over study, where baseline is compared to the intervention, and sham is also compared to the intervention.

The assessment procedure in Sections 7.3.3 and 7.3.4 will therefore be repeated 3 times, like is depicted in Figure 4.

The first condition is the baseline condition without orthosis. In the second and third condition, the sham device and anti-tremor orthosis will be tested, in randomized order. The CRF software determines the randomization.

The investigator will fasten the orthosis as explained in Section 6.5. The IMU sensors can stay attached at the same places as in the baseline condition.

## 7.3.6 Satisfaction assessment

Once the data for either the sham or intervention has been collected, the investigator removes the device from the patient's arm. The patient is then asked to fill out the satisfaction questionnaire (D-QUEST). Satisfaction is collected after both the sham and the investigational device. The investigator can help if the patient has writing difficulties. Before the patient leaves, all questionnaires will be checked thoroughly on completeness to prevent missing data.

## 7.3.7 Reporting Adverse Events

During the entire visit, the principal investigator will report every observed adverse event using the Adverse Event (AE) Report Form. This form will specify the severity, relation to the study intervention, the taken action, the outcome, the expectancy and whether the event was a SAE of the AE. If SAEs have been observed, they must be reported by the sponsor

though the web portal of *ToetsingOnline*, more information can be found in Section 8.

## 7.3.8 Health-related Quality of Life

After the first condition (baseline) health-related QoL will be assessed using the EQ-5D-5L questionnaire. This questionnaire gives insight in the patient's perception of their health-related QOL, this could possibly influence their satisfaction of the anti-tremor orthosis.

## 7.4 Withdrawal of individual subjects

Subjects can leave the study at any time for any reason if they wish to do so and revoke their consent without any consequences. The investigator can decide to withdraw a subject from the study for urgent medical reasons or in case the neurologist deems the patient not capable of participation for any physical or psychological reason.

In case of withdrawal, all patient data that was gathered during the course of the investigation will be – if possible - anonymized for privacy reasons.

## 7.5 Replacement of individual subjects after withdrawal

Depending on the number of subjects that are recruited, withdrawal of a patient will either lead to replacement of the subject or not. In case the sample size drops due to withdrawal, new patients will be included. We do not expect a high drop-out rate, since the study is not time consuming or demanding a lot of effort from a patient, nor are big risks associated with participation.

## 7.6 Follow-up of subjects withdrawn from treatment

Subjects that withdraw from the study, will not be followed or contacted for future research. Data that was already collected until the moment of withdrawal, will be used for the study.

## 7.7 Premature termination of the study

The study will terminate before finishing only in highly exceptional cases when:

- the judgment of the METC that assessed the investigation is irrevocably withdrawn.
- it is plausible that the research should be terminated in the interests of the health of the subjects.

• it appears that continuation of the study serves no scientific goal and that the METC confirms this.

- one of the parties is declared bankrupt or when bankruptcy is demanded.
- the principal researcher is no longer capable of performing the tasks he is assigned to and no replacement with mutual consent can be found.

• one of the parties do not fulfil the obligations as stated in the agreements and these obligations are not fulfilled after 30 days after receipt by the failing party of a written request for fulfilment.

## 8. SAFETY REPORTING

## 8.1 Temporary halt for reasons of subject safety

In accordance to section 10, subsection 4, of the WMO, the sponsor will suspend the study if there is sufficient ground that continuation of the study will jeopardise subject health or safety. The sponsor will notify the accredited METC without undue delay of a temporary halt including the reason for such an action. The study will be suspended pending a further positive decision by the accredited METC. The investigator will take care that all subjects are kept informed.

## 8.2 AEs and SAEs

## 8.2.1 Adverse events (AEs)

Adverse events are defined as any undesirable experience occurring to a subject during the study, whether or not considered related to the investigational product or trial procedure. All adverse events reported spontaneously by the subject or observed by the investigator or his staff will be recorded using the *Adverse Event (AE) report form* (Dutch: meldingsformulier) that can be found in Appendix II.

## 8.2.2 Serious adverse events (SAEs)

A serious adverse event is any untoward medical occurrence or effect that

- results in death;
- is life threatening (at the time of the event);
- requires hospitalisation or prolongation of existing inpatients' hospitalisation;
- results in persistent or significant disability or incapacity;
- is a congenital anomaly or birth defect; or
- any other important medical event that did not result in any of the outcomes listed above due to medical or surgical intervention but could have been based upon appropriate judgement by the principal investigator.

An elective hospital admission will not be considered as a serious adverse event. The investigator will report all SAEs to the sponsor without undue delay after obtaining knowledge of the event. The sponsor will report the SAEs through the web portal ToetsingOnline to the accredited METC that approved the protocol, within 2 days of first knowledge for SAEs that result in death or are life threatening followed by a period of maximum of 2 days to complete the initial preliminary report. All other SAEs will be reported within a period of maximum 5 days after the sponsor has first knowledge of the serious adverse events.

## 8.3 Follow-up of adverse events

All AEs will be followed until they have abated, or until a stable situation has been reached. Depending on the event, follow up may require additional tests or medical procedures as indicated, and/or referral to the general physician or a medical specialist. SAEs need to be reported till end of study within the Netherlands, as defined in the protocol

## 8.4 Data Safety Monitoring Board (DSMB)

Does not apply to this study.

## 9. STATISTICAL ANALYSIS

## 9.1 Primary study parameters

The primary objective of this study is to evaluate the effects of the STIL anti-tremor orthosis on the tremor severity and amplitude in the forearm.

## Tremor severity using TETRAS

Tremor severity is assessed by the neurologist in 7 rated TETRAS tasks using TETRAS' rating scale. This endpoint scores will be compared over the two conditions (baseline vs. intervention & sham vs. intervention).

A two-tailed matched pairs t-test will be used to analyze differences in tremor severity over these conditions.

First, the data will be tested for normal distribution. Then, the t-test will be applied to check for a difference in tremor severity in the two conditions. If the data is not normally distributed, 4 Wilcoxon matched pair tests will be performed. In this way, not only can the effects of the intervention be validated, but also the effects of the sham device (e.g. the effect of weight of the orthosis on tremor severity).

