- Steadi-One; a mechanical device which uses of fluids for reducing amplitude of motions . Results show those patients who improved by kinematic analysis had a 0.81-point score clinical improvement. There was a 0.57-point improvement in dynamic tasks based on the Fahn-Tolosa-Marin clinical rating scale (FTM) .
- The study of Lin et al. (2018) evaluated the CALA wrist device that used nerve stimulation to reduce hand tremor. This study showed a tremor amplitude reduction of 60% ± 8.4% (n = 23) which was significantly greater in the treatment than in the sham group .
- The Liftware Spoon, a handheld assistive device which also makes use of active cancellation of tremor, reduced the tremor amplitude with 73% ± 13% (n = 11) .
- The out-of-phase wrist device that uses electrical stimulation of antagonistic muscle of Maneski et al (2011) showed a significant reduction in tremor amplitude of 67% ± 13% (n = 7)
   .

Given the fact that the effects showed in other anti-tremor device studies were large, and the patients only benefit from a device that has a large effect on their tremor, the effect size d 0.8 was chosen .

An example calculation where the orthosis reduces 4 points (out of 28 total) on the TETRAS scale, assuming a standard deviation of 5 for both groups, generates this effect size of 0.8 (see Figure 3).

In total, 4 conditions will be compared with 2 different outcome measures; baseline vs. intervention (TETRAS), sham vs. intervention (TETRAS), baseline vs. intervention (IMU data) and sham vs. intervention (IMU data).

Taking into account a worst-case scenario of type 1 errors accumulation over the 4 testing conditions, a Bonferroni correction of alpha = 0.05/4 = 0.0125 is used.

The power value of 0.8 has been used, since this value is common practice in medical literature.

Using the above-mentioned parameters, it can be concluded that a minimum of 21 patients is needed. In order to compensate for possible drop-outs (10%), 25 patients will be included for this clinical investigation.

If the data is not normally distributed (after log compensation), unlike described in literature, the statistical analyses can also be performed by means of 4 Wilcoxon matched pair tests. This has no consequences for the sample size, since the sample size analysis in such case will result in 22 patients.

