## 7.2 Randomisation, blinding and treatment allocation

Tremor severity will be assessed in three situations: without wearing the orthosis (baseline), with the sham orthosis (sham) and with the anti-tremor orthosis (intervention). An algorithm within the CRF software, which includes the API that is used to acquire the motion data, will randomly determine the order of the sham device and intervention. Only the investigator can see which device is selected, thereby blinding the patient. The investigator will obtain the selected device,

using color-coded tabs, and attach it to the patient's arm/hand. Both the devices will have a comparable look and weight (see *IMDD chapter 1.1.i*).

Tremor amplitude can be affected by adding passive weight. By evaluating the sham device, the effects of the weight of the orthosis on tremor suppression will be taken into account. It is also used to evaluate the possible placebo-effect on tremor reduction. Because the investigator knows which variant is being tested, the data will be placed with the corresponding variant in the digital CRF. The patient will be seated in such way that it is not possible for him/her to view the CRF. This eliminates the need to decode the collected data.

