## Tremor amplitude using IMU data

Tremor amplitude is measured during the performed tasks by taking the data from the IMU that is attached to the fingers. Likewise, this endpoint score will be compared over the two conditions using two-tailed matched pairs t-test, to analyze the difference in tremor amplitude. Again, the data will be checked for normal distribution, and the effect of the sham device will be evaluated.

The mean reduction in tremor severity according to both TETRAS rating and tremor amplitude of the hand are the co-primary endpoints. Sub analyses will be performed to evaluate the effect of the orthosis on these endpoints during the different tasks. This will be done to analyze the effect of the orthosis on specific tremor types: kinetic tremor (eating, drinking, pouring and spiral drawing), postural tremor (forward outstretched posture, lateral wing beating posture) and intention tremor (finger-to-nose).

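### The paired tests in Section 9.1 ignore the randomised device order, which costs power if there is a period effect, and no listed contrast estimates the sham's own effect

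*Protocol*

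**What the plan says.** Section 7.3.5 puts baseline first and then states: "In the second and third condition, the sham device and anti-tremor orthosis will be tested, in randomized order". Section 7.2 leaves the order to an algorithm in the CRF software and describes no balancing.

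For TETRAS, Section 9.1 fixes the test: "A two-tailed matched pairs t-test will be used to analyze differences in tremor severity over these conditions". For amplitude: "this endpoint score will be compared over the two conditions using two-tailed matched pairs t-test". Wilcoxon matched-pair tests are the fallback. No section has a period, sequence or order term.

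The contrasts are fixed in three places. Section 9.1: "This endpoint scores will be compared over the two conditions (baseline vs. intervention & sham vs. intervention". Section 7.3.5: "where baseline is compared to the intervention, and sham is also compared to the intervention". Section 4.4 counts four tests to reach alpha 0.0125; after baseline vs intervention on TETRAS, the list runs "sham vs. intervention (TETRAS), baseline vs. intervention (IMU data) and sham vs. intervention (IMU data". Baseline vs sham is in none of them.

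Section 9.1 nevertheless says that this approach validates not only the intervention, "but also the effects of the sham device (e.g. the effect of weight of the orthosis on tremor severity", and its amplitude paragraph also promises an evaluation of the sham's effect. Section 7.2 adds: "It is also used to evaluate the possible placebo-effect on tremor reduction".

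**The concern.** Sham vs intervention is the only comparison whose order is randomised. Patients repeat the same seven tasks three times, and Sections 7.3.1 and 7.3.2 themselves say that nervousness or stress may increase tremor, so practice, fatigue or calming could plausibly change scores between the two device periods. A plain paired test leaves that change in the residual variance. If the two orders are unequally filled, part of it also enters the estimate. The plan has only 81% power at 21 patients, so there is little to spare.

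The second issue is a mismatch between claim and contrasts. Sham vs intervention isolates the dampers. Baseline vs intervention combines the dampers with everything else about wearing a device. Neither gives the effect of the sham itself, which the protocol says it will evaluate.

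**Working it through.** **Inputs.** From Section 4.4 and its Figure 3: mean difference 4 TETRAS points, SD 5 per condition, correlation 0.5, two-sided alpha 0.05/4 = 0.0125, power 0.80, minimum 21 patients, 25 enrolled. Assumed, because the protocol gives no figure: a shift λ of 2 or 3 points between the first and second device period.

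**The plan's own figure.** The SD of the difference is √(25 + 25 − 2·0.5·25) = 5, so dz = 4/5 = 0.8. With n = 21, the noncentrality is 0.8·√21 = 3.666, the critical t on 20 df is 2.744, and power is 0.8100. The stated 21 reproduces.

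**Order model.** Let d = sham score − orthosis score. Its mean is 4 + λ if the orthosis comes first (n₁ patients) and 4 − λ if the sham comes first (n₂ patients).

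- Plain mean of d: expectation 4 + λ(n₁ − n₂)/n. The expected sample variance is 25 + λ²·4n₁n₂/[n(n − 1)]. At 11:10 the multiplier is 440/420 = 1.048, so the SD rises from 5 to √(25 + 4.19) = 5.40 at λ = 2 and to √(25 + 9.43) = 5.87 at λ = 3.
- Adjusted estimate: the average of the two sequence means, free of λ. SE = ½·5·√(1/n₁ + 1/n₂). At 11:10 this is 2.5·√0.1909 = 1.092, so the noncentrality is 4/1.092 = 3.66 on 19 df and power is 0.805.

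**Simulated power** (200,000 trials per setting, n = 21, alpha 0.0125):

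| Shift λ | 11:10, plain: odd patient favourable / unfavourable / average | 11:10, adjusted | Simple randomisation, plain | Simple randomisation, adjusted |
|---|---|---|---|---|
| 0 | 0.81 / 0.81 / 0.81 | 0.805 | 0.81 | 0.78 |
| 2 | 0.77 / 0.72 / 0.75 | 0.805 | 0.74 | 0.78 |
| 3 | 0.71 / 0.62 / 0.67 | 0.805 | 0.66 | 0.78 |

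**Type I error of the plain test.** At 11:10 it is about 0.75% for λ = 2 and 0.4% for λ = 3, which is conservative. Under simple randomisation it stays at 1.2 to 1.3%.

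**Uneven split.** Under simple randomisation, P(8:13 or worse) = 2·P(Bin(21, ½) ≤ 8) = 0.38. At exactly 8:13, a 2-point shift moves the estimate by 2·5/21 = 0.48 points, which is 0.48/4 = 12% of the 4-point effect.

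**The contrasts.** Subtracting the two planned mean differences, (baseline − intervention) − (sham − intervention), gives the mean of baseline − sham. A confidence interval does not follow from the two results, because it needs the within-patient baseline − sham differences, and none is planned. If the contrast joined the Bonferroni family for both endpoints there would be six tests: alpha 0.05/6 = 0.0083, 23 evaluable patients, 23/0.9 = 25.6, so 26 enrolled rather than 25.

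**The case against.** The best defence is that randomised order makes the plain paired test valid, so a period term is an efficiency choice that could be left to an analysis plan. Much of this stands. A reader might infer a wrong standard error and false positives, but the calculations do not support that: type I error is at or below its nominal level to within simulation error. Under simple randomisation the standard error properly includes the variation from order, and the estimate is unbiased over the randomisation. The 0.48-point shift is conditional on one realised split.

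The size of the loss is also assumption-driven. Shifts of 2 and 3 points are 50% and 75% of the target effect. Quoting only the unfavourable direction of an 11:10 split (0.72 and 0.62) would overstate the loss. With no shift under simple randomisation, adjustment lowers power from 0.81 to 0.78. If all 25 enrolled patients are evaluable, planned power with no shift is 0.89.

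On the sham, the primary objectives concern the orthosis alone. Section 5.1 uses the sham to remove the influence of weight and to validate the dampers, which sham vs intervention does.

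What the defence does not answer is that the protocol itself fixes the tests and contrasts, and states in Section 9.1 that these show the sham's own effect. They do not.

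**Conclusion.** The point holds in two limited parts.

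First, the planned test of sham vs intervention is valid but inefficient if there is a period effect. The loss at 21 patients is about 5 percentage points of power for an assumed 2-point shift and about 14 for 3 points with an 11:10 split. Under simple randomisation it is about 4 and 12 points. An uneven split also shifts the realised estimate. These figures rest on the protocol's SD of 5 and effect of 4, and on assumed period shifts. The sample size is correct for the tests as planned.

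Second, the claim that the sham's effect is evaluated is not met by any listed contrast. It would be tempting to conclude that adding baseline vs sham would isolate weight or placebo. The design does not allow that: baseline always comes first, so the contrast is confounded with period, and it cannot separate weight from placebo. The sequence adjustment does not cure this, because only the order of the two devices is randomised.

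**What to change.** **Sham vs intervention.** For TETRAS and for log amplitude, estimate the device effect as the average of the two sequence means of the paired differences (equivalently, a model with patient, period and device), and report it with its interval. This assumes no carry-over between devices, in line with Section 6.4, which expects no effect after removal. The cost is wording only. If there is no period effect, the adjustment loses about 0.5 percentage points of power with balanced order and about 3 under simple randomisation.

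**Baseline vs sham.** Report it for both endpoints as an estimate with confidence interval, outside the confirmatory family, so that alpha 0.0125 and the 25 patients stand. State beside it that baseline is always first, so the contrast is confounded with period and cannot separate weight from placebo. All three conditions are already measured, so no new data are needed. Otherwise, withdraw the statements in both parts of Section 9.1 that the sham's effect is evaluated, and align Section 7.2.
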